**Table 3. Example of Calculation of Stool Frequency Subscore at Post-baseline for Mayo Scorea**

		Diary Day Looking Back From Endoscopy Day b							Anchor Day	Validated Days for Calculation	Average Subscore	Average Subscore – Normal SF	Final SF Subscore
		Normal SF c		-7	-6	-5	-4	-3	-2	-1	V-Day 1		
		3 Jan	4 Jan	5 Jan	6 Jan	7 Jan	8 Jan	9 Jan	10 Jan				
Diary 1	15	16	20	17	15	19	21	18	X	-4, -3, -2,	18.3 ~18	18-15=3	2
Diary 2	18	M	M	M	M	15	18	M	X	-3, -2	Missing	Missing	Missing d
Diary 3	11	M	M	M	M	8	M	M	X	-3	Missing	Missing	Missing d
Diary 4	7	M	11	M	11	15	10	M	X	-4, -3, -2	12	12-7=5	3

M = missing; pMCS = partial Mayo score; SF = stool frequency; X = non-evaluable

a For the calculation of pMCS, consecutive days for SF are not required in the week prior to the visit.b Days are named related to anchor day – Visit Day; The diary data collected prior/day of endoscopy will be discarded as endoscopy and its preparation may impact the validity of the diary data.c Normal SF is defined as the average number of stools during patient remissiond Final subscore missing due to missing consecutive day(s) in the week prior to the endoscopy day (not including the bowel preparation day).

For Mayo RB Subscore, the RB average will be rounded to the nearest integer to match the following scorings:

- 0 No blood seen
- 1 Streaks of blood with stool less than half the time
- 2 Obvious blood (more than just streaks) or streaks of blood with stool most of the time
- 3 Blood alone passes

**Table 4. Example of Calculation of Rectal Bleeding Subscore at Post-baseline for Mayo Scorea**

Examples	Diary Day Looking Back From Endoscopy Day b							Anchor Day	Validated Days for Calculation	Average Subscore	Final Subscore	
	Normal SF c		-7	-6	-5	-4	-3	-2	-1	V-Day 1		
	3 Jan	4 Jan	5 Jan	6 Jan	7 Jan	8 Jan	9 Jan	10 Jan				
Diary 1	M	M	2	2	1	2	2	X	-4, -3, -2,	1.67	2	
Diary 2	M	M	M	M	0	1	M	X	-3, -2	Missing	Missing c	
Diary 3	M	M	M	M	0	M	M	X	-3	Missing	Missing c	
Diary 4	M	2	M	2	1	1	M	X	-4, -3, -2	1.33	1	
Dairy 5	M	M	M	M	0	M	1	X	-3, -1	Missing	Missing c	

M = missing; pMCS = partial Mayo score; RB = rectal bleeding; X = non-evaluable

a For the calculation of pMCS, consecutive days for RB are not required in the week prior to the visit.

---

b Days are named related to anchor day – Visit Day; The diary data collected prior/day of endoscopy will be discarded as endoscopy and its preparation may impact the validity of the diary data.

c Final subscore missing due to missing consecutive day (s) in the week prior to the endoscopy day (not including the bowel preparation day).

### 6.1.2 GEBOES SCORE

The Geboes scoring system is a stepwise ordinal grading system for histological assessment of disease severity in UC ([Appendix C](#)). The scoring system progressively grades disease severity by assessing 7 histological items. These 7 histological items are: architectural changes (Grade 0), chronic inflammatory infiltrate (Grade 1), lamina propria neutrophils and eosinophils (Grade 2), neutrophils in epithelium (Grade 3), crypt destruction (Grade 4), and erosions or ulcerations (Grade 5). Each grade of the score is divided in 4 subgrades, based upon the severity of tissue abnormalities or the extent of cell infiltration. The Geboes score ranges from 0 to 5.4, with higher scores indicating more severe inflammation; typically, UC is defined as active histological inflammation with a Geboes score of  $\geq 2$ . The overall Geboes score is calculated as the highest grade without a zero (i.e., absence) subscore, unless all grades are zero in which case the score will be 0.0. For example, if Grade 3: Neutrophils in lamina propria is checked as “< 50% crypts involved” (3.2), Grade 4: Crypt destruction is checked as “None” (4.0), and Grade 5: Erosions and ulcerations is checked as “No erosion, ulceration, or granulation tissue” (5.0), the subject will be assigned a final Geboes score of 3. If a subject has either abnormalities in lamina propria eosinophils or lamina propria neutrophils, they will be assigned a score of 2.

### 6.1.3 ROBARTS HISTOPATHOLOGY INDEX

The Robarts Histopathology Index (RHI) measures histological disease activity in patients with UC ([Appendix D](#)). The RHI is divided into 4 categories: 1) the extent of chronic inflammatory cell infiltration, 2) neutrophils in the lamina propria, 3) neutrophils in the epithelium, and 4) erosions and ulceration. Each item has 4 levels and is scored from 0 to 3 and multiplied by a weighting factor and summed to give the overall RHI score. The RHI score ranges from 0 to 33, with higher scores being indicative of more severe disease. If any one component of the RHI is found to be missing, then the overall RHI score will be set as missing. The equation used to calculate the RHI is shown below.

**RHI** = 1 x chronic inflammatory infiltrate level + 2 x lamina propria neutrophils + 3 x neutrophils in epithelium + 5 x erosion or ulceration\*

\*A Geboes Grade 5 component score of  $>1$  is reduced by 1 point prior to be incorporated into the RHI calculation.

### 6.1.4 UC-100

UC-100 is used to assess UC disease activity and is derived from the MCS and RHI variables. The UC-100 ranges from 1 (no disease activity) to 100 (severe disease activity). If any one component score of UC-100 is found to be missing, then the entire test score will be set as missing.

Composite UC-100 score:  $(1 + 16 \times SF + 6 \times MES + 1 \times RHI)$ .

## 6.2 EFFICACY ENDPOINTS

### 6.2.1 DICHOTOMOUS EFFICACY ENDPOINTS

The definitions of the dichotomous efficacy endpoints are presented in [Table 5](#).

**Table 5. Definition of Binary Endpoints**

Binary Endpoint	Measure	Definition	Analysis Timepoint
Clinical Remission	Modified MCS	Modified MCS (SF subscore $\leq 1$ [with or without decrease], RB subscore of 0, and MES of $\leq 1$ [where the definition of 1 does not include friability])	CCI
Endoscopic Improvement	MES	MES of less than or equal to 1	
Clinical Response	Modified MCS	Decrease in modified MCS of $\geq 2$ and a relative $\geq 30\%$ from baseline, and a decrease of the Mayo RB subscore of at least 1 point or an absolute subscore for RB of 0 or 1	
Symptomatic Remission	SF, RB	SF subscore 0 or 1 with a decrease of $\geq 1$ point from baseline, and RB subscore of 0	
Symptomatic Response	SF, RB	$\geq 30\%$ decrease from baseline in composite sum of SF and RB subscores	
Endoscopic Remission	MES	MES of 0	
Histologic Remission	GHI, RHI	Geboes index score $< 2B.1$ or RHI score $\leq 3$ , with subscores of 0 for lamina propria neutrophils and 0 for neutrophils in epithelium	
Histologic Response	RHI	Change from baseline RHI $\geq 7$ points	
Mucosal Healing	GHI, MES	GHI $< 2$ and endoscopic remission (MES of 0)	

GHI = Geboes histologic index; MCS = Mayo score, MES = Mayo endoscopic subscore; RB = rectal bleeding; RHI = Robarts Histopathology Index; SF = stool frequency

#### 6.2.1.1 Statistical Methods for Dichotomous Efficacy Endpoints

The proportion of subjects achieving each of the dichotomous efficacy endpoints defined in [Table 5](#) will be summarized by treatment group using frequency distribution. To compare the proportion of subjects at a timepoint [CCI](#) the Cochran-Mantel-Haenszel (CMH) method will be used, and an exact 95% CI will be estimated. Missing values in the categorical endpoints will be imputed as non-responders. All dichotomous efficacy endpoints will be listed in by-subject listings.

#### 6.2.2 CONTINUOUS EFFICACY ENDPOINTS

The definitions of the continuous efficacy endpoints (mean change from baseline) are listed in [Table 6](#).

**Table 6. Definition of Continuous Efficacy Endpoints**

Measure	Definitions	Analysis Timepoint
mMCS	Mean changes in mMCS from baseline	CCI
MCS	Mean change in total MCS	
pMCS	Mean changes in pMCS from baseline	
RHI	Mean change in RHI from baseline	
UC-100	Mean change in UC-100 score from baseline	
pMCS	Mean changes in pMCS from baseline	

MCS = Mayo Score; mMCS = modified Mayo score; pMCS = partial Mayo Score; RHI = Robarts Histopathology Index; UC = ulcerative colitis

#### 6.2.2.1 Statistical Methods for Continuous Efficacy Endpoints

Continuous endpoints will be summarized by treatment group using descriptive statistics of the values at each visit and the change from baseline to each post-baseline visit. For continuous endpoints at only one post-baseline visit, an analysis-of-covariance (ANCOVA) will be used for analysis. The changes from baseline will be compared between treatments adjusted for the baseline value.

For continuous data with repeated measures post-randomization, mixed-model-repeated measure (MMRM) will be used for analysis. The model will include fixed effects for treatment, visit, baseline value, and treatment-by-visit interaction. This analysis will be conducted by maximum likelihood methods using the SAS PROC MIXED procedure. Least squares means and 95% CIs will be provided for each assessment timepoint.

All collected efficacy data will also be presented in a by-subject listing.

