2.2.3 Exploratory Endpoints

- Mean change from baseline in modified Mayo Score at Week 12
- Mean change from baseline in total Mayo Score at Week 12
- Mean change from baseline in partial Mayo Score at Weeks 2, 4, 6, 8, 10, and 12
- Mean change from baseline in Roberts Histopathology Index (RHI) score at Week 12
- Mean change from baseline in UC-100 score at Week 12
- Mean change from baseline in fecal calprotectin (FC) at Weeks 4 and 12
- Mean change from baseline in high sensitivity C-reactive protein (hs-CRP) levels at Weeks 2, 4, 8, and 12
- Mean change from baseline in patient-reported outcome (PRO) measures at Week 12
 - Inflammatory Bowel Disease Questionnaire (IBDQ)
 - Short Form-36 (SF-36)
- Proportion of subjects achieving clinical remission at Week 12
- Proportion of subjects achieving endoscopic improvement at Week 12
- Proportion of subjects achieving clinical response at Week 12
- Proportion of subjects achieving symptomatic remission at Weeks 2, 4, 6, 8, 10, and 12
- Proportion of subjects achieving symptomatic response at Weeks 2, 4, 6, 8, 10, and 12
- Proportion of subjects achieving endoscopic remission at Week 12
- Proportion of subjects achieving histologic remission at Week 12
- Proportion of subjects achieving histologic response at Week 12
- Proportion of subjects achieving mucosal healing at Week 12
- Change from baseline in partial Mayo Score beyond Week 12
- Incidence and characterization of TEAEs and laboratory abnormalities beyond Week 12
- Changes in PT101- and UC-associated biomarkers

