9.3.1.6 Adjustments for Covariates

Detailed methodology will be provided in the SAP.

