9.3.4 Safety and Efficacy Analyses

Progression from Cohort 1 to Cohort 2 per protocol will be based on DRC recommendations from all available unblinded safety and PK/PD data reviewed from Cohort 1 along with all unblinded safety data (all 8 subjects [PT101:PBO; 6:2] up to one week after ^{CCI}

^{CCI}
^{CCI}

Recommendations from the DRC may also include modification to the study design, including but not limited to assessment of a lower dose or repeating a dose/dosing regimen, changes to subject safety monitoring assessments or addition of sampling timepoints. ^{CCI}

^{CCI}
^{CCI}

DRC will review all safety and available PK/PD ^{CCI} ons for the next cohort (Cohort 3) regarding study continuation, dose escalation per protocol or any modification to the study design. Moving sequentially from Cohort 1 through 3 will require demonstration of adequate safety, guided by the in-cohort stopping rules and the cohort progression criteria (see [Section 3.1.1.4](#)).

The safety of each dose level will be evaluated by examining the probability of experiencing a DLT (as defined in [Section 3.1.1.3](#)) based on a Bayesian Logistic Regression Model (BLRM) ([Neuenschwander, 2008](#)) and the incidence of TEAEs, TESAEs, treatment-related TEAEs, and treatment-related TESAEs.

A dose will be considered safe if the estimated probability (posterior median) of experiencing a DLT is ≤ 0.25 . The MTD will be determined according to the following rules:

CCI

CCI

The selected dose may not exceed the Escalation With Overdose Control (EWOC) threshold: the posterior probability of overdosing, either excessive or unacceptable toxicity ≤ 0.25 .

The dose level(s) and dosing regimen with the best benefit/risk profile based on the totality of safety and efficacy data at Week 12 will inform selection for future clinical development.

For efficacy endpoints, to compare the proportion of subjects at a timepoint (i.e., Week 12), the Cochran-Mantel-Haenszel (CMH) method will be used and an exact 95% confidence interval will be estimated. CCI

CCI

For continuous data in terms of change from baseline to Week 12, analysis-of-covariance (ANCOVA) on last-observation-carried-forward (LOCF) will be used for analysis. For continuous data with repeated measures postrandomization, mixed-model-repeated measure (MMRM) will be used for analysis. Details on covariates will be specified in the SAP.

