### 3 STUDY DESIGN

#### 3.1 SUMMARY OF STUDY DESIGN

The study will enroll up to approximately 60 subjects with mildly to severely active UC in up to 6 cohorts of 10 subjects each (randomized 4:1 [PT101:placebo]) in a multiple ascending doses design. There will be 3 planned cohorts (Cohorts 1 to 3) and up to 3 optional cohorts (Cohorts 4 to 6). Subjects in Cohort 1 will receive PT101 or placebo [REDACTED] CCI [REDACTED] for a total of [REDACTED] CCI [REDACTED] Cohorts 2 and 3 will receive PT101 or placebo [REDACTED] CCI [REDACTED] for a total of [REDACTED] CCI [REDACTED]

period. Subject randomization will be stratified by prior advanced therapy use (yes or no). Enrollment of subjects with a prior history of inadequate response, loss of response, or intolerance to 2 advanced therapies as assessed by the Investigator will be capped at 20% of subjects per cohort.

Subjects who have achieved clinical response (based on the modified Mayo Score [mMCS] using the endoscopic subscore [MES] derived by the Investigator) at CCI will be eligible to enter the continued blinded treatment (CBT) phase of the study. Subjects in the CBT phase will receive the same treatment allocation (PT101 or placebo) as received during the initial blinded treatment (IBT) phase; subjects who received PT101 will continue receiving PT101 at the same dose/regimen. Corticosteroid tapering will be initiated at CCI of the IBT phase for subjects entering the CBT phase. Subjects who enter the CBT phase will receive their first dose of blinded study drug on CCI for both dosing regimens CCI

CCI Subjects who do not achieve clinical response at CCI will have the option to enter an open-label (OL) phase of the study. Subjects in the OL phase will receive PT101 at the same dose/regimen as received by subjects in their cohort during the IBT phase. Subjects participating in the OL phase who achieve a clinical response using the partial Mayo Score (pMCS) at CCI of the OL phase will also undergo corticosteroid tapering. Subjects who do not achieve a clinical response using the pMCS at CCI of the OL phase may continue on open-label treatment if it is considered in the best interest of the subject at the discretion of the investigator. Subjects who enter the OL phase will receive their first dose of PT101 on CCI for both dosing regimens CCI

Subjects with insufficient data to assess clinical response at CCI of IBT will not be eligible to enter the CBT or OL phases and will be discontinued from the study.

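### The stratification factor, prior advanced therapy use, is missing from the SAP's ANCOVA and MMRM; the intervals stay valid but may be wider than needed, and the SAP should also say whether the MMRM uses ML or REML

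*SAP*

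**What the plan says.** SAP 3.1 states: "Subject randomization will be stratified by prior advanced therapy use (yes or no"; protocol 3.1 says the same. The protocol leaves covariates to the SAP twice: section 9.3.1.6 says "Detailed methodology will be provided in the SAP" and section 9.3.4 says "Details on covariates will be specified in the SAP".

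SAP 6.2.2.1 then sets out two models. For endpoints with a single post-baseline visit it plans an ANCOVA: "The changes from baseline will be compared between treatments adjusted for the baseline value". For repeated measures it plans an MMRM: "The model will include fixed effects for treatment, visit, baseline value, and treatment-by-visit interaction". On estimation it says "This analysis will be conducted by maximum likelihood methods using the SAS PROC MIXED procedure", and on reporting, "Least squares means and 95% CIs will be provided for each assessment timepoint". It names no covariance structure and no degrees-of-freedom method. Among the measures in SAP Table 6, the MMRM concerns the partial Mayo score; protocol 2.2.3 lists "Mean change from baseline in partial Mayo Score at Weeks 2, 4, 6, 8, 10, and 12".

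Prior advanced therapy use does appear elsewhere in the SAP. It is a baseline characteristic in 5.3 and an optional covariate in the supplementary logistic regression of 6.2.3. It is in neither continuous model, and SAP 14, which lists changes from the protocol, does not explain why.

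**The concern.** When allocation is balanced within strata, the between-stratum variation drops out of the true variability of the treatment difference. A model without the stratum still counts that variation as residual noise. If the factor is prognostic, the standard error is then too large and the interval too wide. With about 30 subjects, and two placebo subjects per cohort, precision is scarce and the factor is already collected.

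The estimation wording matters in the other direction. ML estimates variances without allowing for the fixed effects that were fitted, so with few subjects and several arms its standard errors are smaller than those from REML.

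What is at stake is the width and labelling of the 95% intervals. No visible decision rule uses them, although protocol 9.3.4 lets the totality of Week 12 safety and efficacy data inform dose selection.

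**Working it through.** The plan gives no precision figure for these endpoints. Its only power statement concerns Treg counts, and the variability behind that statement is not visible, so there is no figure of the plan's own to reproduce.

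**Inputs from the documents.** 8 PT101 and 2 placebo subjects per dose level; at least 30 subjects evaluated at Week 12 in three planned cohorts; about 60 subjects in up to six cohorts; six partial Mayo visits. **Assumed.** Placebo pooled across cohorts (protocol 9.3.4 reads that way; the SAP is silent); blocks of five within stratum and cohort; 30% or 50% of subjects with prior advanced therapy; a difference between strata of d residual SDs.

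**1. Omitting the factor from the ANCOVA.** Width of the 95% interval without the factor divided by width with it, from simulation (6,000 replicates per setting):

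| N, share with prior therapy | d = 0 | 0.25 | 0.5 | 0.75 | 1.0 |
|---|---|---|---|---|---|
| 30, 50% | 0.990 | 0.998 | 1.022 | 1.061 | 1.114 |
| 30, 30% | 0.988 | 0.994 | 1.016 | 1.048 | 1.092 |
| 60, 50% | 0.995 | 1.002 | 1.026 | 1.063 | 1.115 |
| 60, 30% | 0.994 | 1.000 | 1.019 | 1.052 | 1.094 |

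A hand check agrees. With share p, omission inflates the residual SD by √(1 + d²p(1 − p)). For p = 0.5 and d = 0.5 this is √1.0625 = 1.031; multiplied by the ratio of 0.990 at no effect it gives 1.021. For d = 1.0 it is √1.25 = 1.118, times 0.990 = 1.107.

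Coverage without the factor at N = 30 was 94.4% to 96.7%. The cost of including a factor with no effect is 1/0.990 to 1/0.988, about 1%.

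**2. A single cohort, 8 against 2.** The ratio is 0.946 (50%) or 0.938 (30%) at d = 0, so including the factor costs 6% to 7%. It breaks even near d = 0.75 (1.013 and 1.000). No visible text plans such a comparison.

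**3. ML against REML in the MMRM.** With complete data, unstructured covariance and g arms, the ratio of standard errors is √((N − g)/N) without a baseline term and √((N − g − 1)/N) if baseline uses one degree of freedom at every visit. The SAP's single baseline slope lies between these.

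- N = 30, three doses and placebo (g = 4): √(26/30) = 0.931 and √(25/30) = 0.913, shortfalls of 6.9% and 8.7%. Simulation with a single slope gives about 8%.
- N = 60, six doses and placebo (g = 7): √(53/60) = 0.940 and √(52/60) = 0.931, shortfalls of 6.0% and 6.9%. Simulation gives 6.4% to 6.7%.
- N = 30, all PT101 pooled (24 against 6, g = 2): √(28/30) = 0.966 and √(27/30) = 0.949, shortfalls of 3.4% and 5.1%. Simulation gives 4.3%.

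With an assumed 15% dropout, the N = 30 four-arm shortfall rises to 8.8%.

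**4. Both points together.** For the MMRM at N = 30 (50% prior therapy, exchangeable visit correlation 0.5), the width of ML without the factor divided by REML with the factor is 0.916, 0.945 and 1.029 at d = 0, 0.5 and 1.0. ML coverage is 92.6%, 93.5% and 94.6%. REML with the factor covers 94.3%, 95.1% and 94.8%.

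**The case against.** The strongest reply is that nothing here is an error. The protocol delegated covariates to the SAP, the SAP chose them, and a baseline-only ANCOVA with about 30 subjects is defensible. The gain from adding the factor is 2% or less up to an assumed 0.5 SD; the larger gains need a stratum effect of about 0.75 to 1.0 residual SD, which the documents do not support. This stands, and it is why the point is offered as an improvement.

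A reader might infer that leaving out a stratification factor invalidates the intervals or inflates false positives. It does neither; at worst the intervals are conservative.

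A reader might also infer that the partial Mayo standard errors are 7% to 8% too small. The documents do not support that as it stands. The SAP wording covers REML as well as ML, and the size depends on arms, pooling and sample size. ML below REML is also not the same as error against the truth: where the omitted factor is strongly prognostic, the two effects largely cancel (step 4).

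Finally, SAP 6.2.1.1 names no stratum for the CMH method, which might suggest an unstratified analysis. The protocol text directly after its own CMH sentence is redacted and may name one, so no defect is claimed there.

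One limit of the working also stands. The MMRM coverage figures use t intervals on N − arms − 1 degrees of freedom with complete data; Kenward-Roger itself was not simulated.

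**Conclusion.** The omission from the ANCOVA and MMRM is plain in the visible text and unexplained. Its consequence is a possible loss of precision: at 30 subjects with pooled placebo, about 2% in interval width at an assumed 0.5 SD and 9% to 11% at 1.0 SD, against a cost of about 1% if the factor carries no information.

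The estimation point is secondary and conditional. If ML is meant, the standard errors fall about 6% to 8% below REML under the assumptions in step 3 (complete data, separate doses, pooled placebo, 30 to 60 subjects), and about 4% below if all PT101 doses are pooled. If REML is meant, only the wording needs attention.

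The efficacy endpoints are exploratory (protocol 2.2.3) and their analyses descriptive (protocol 9.3.4), so both are low-priority improvements.

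**What to change.** In SAP 6.2.2.1:

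- Add prior advanced therapy use (yes/no) as a fixed effect in the ANCOVA and the MMRM wherever placebo is pooled across cohorts, and state that it is pooled.
- Leave the factor out of any single-cohort comparison with about two placebo subjects.
- State that the MMRM uses REML with Kenward-Roger degrees of freedom, and name the covariance structure. If REML was already intended, say so.

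In SAP 6.2.1.1, the sponsor may simply confirm the same factor as the CMH stratum.

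No new data are needed. The factor uses one degree of freedom, about 1% of interval width at 30 subjects and about 0.5% at 60 if it is not prognostic; naming REML costs nothing. If the database is already locked, SAP 1.1 provides for documenting the change and its rationale in the clinical study report.
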